7.3 Clinical Laboratory Assessments

Clinical laboratory tests will be obtained at the time points presented in Appendix A. The incidence of treatment-emergent laboratory abnormalities will be summarized by severity and treatment group. Continuous clinical laboratory values will be summarized by presenting descriptive statistics of raw data and change from baseline values at each time point for each treatment arm.

Laboratory parameter results from unscheduled visits will be excluded from table summaries but will be included in data listings. When there are repeat measurements for a given visit, only the last measurement will be used in the table summaries.

Listings will include flags for values outside of the reference ranges, and clinical significance if a laboratory result is deemed abnormal, if available. The biomarker analysis is described separately

in Section 6.2.2.

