## APPENDIX 1. SCHEDULE OF EVENTS

	Screening	Treatment Period a							EoT/ET	Phone Call b	Phone Call b
		Baseline Day 1	Day 3	Day 5	Day 7	Day 10 c	Day 14	Day of Hospital Discharge			
	Day -3 to Day -1										
Informed consent	X										
Medical history	X										
Demographics (age, sex, race)	X										
SARS-CoV-2 infection by RT-PCR or COVID-19 tests authorized under EUA	X										
Serum pregnancy test (for women only)	X	X						X	X		
Check inclusion and exclusion criteria	X	X									
Complete physical examination (including height and weight) d	X										
Targeted physical examination d		X	X	X	X	X	X				
Randomization		X									
	X	X	X	X	X	X	X	X			
Ventilator utilization e											
	X	X	X		X			X	X		
											
Vital signs g	X	X	X	X	X	X	X	X			
	X	X	X	X	X	X	X	X			
Confirm daily conduct of vital signs and safety labs h											
Hematology g,h	X	X	X	X	X	X	X	X			
Clinical chemistry g,h	X	X	X	X	X	X	X	X			
Coagulation (INR) g,h	X	X	X	X	X	X	X	X			
Pharmacokinetic sample plasma i		X			X			X	X		

	Screening	Treatment Period a							EoT/ET	Phone Call b	Phone Call b
		Baseline Day 1	Day 3	Day 5	Day 7	Day 10 c	Day 14	Day of Hospital Discharge			
	Day -3 to Day -1										
Plasma biomarker samples		X	X		X		X	X			
Serum biomarker samples		X	X		X		X	X			
Urinalysis (dipstick, followed up by micro if abnormal)	X	X	X	X	X	X	X	X			
Adverse events											
Concomitant medications											
Study drug administration											
Hospital and ICU utilization e											
Vital status									X	X	X

eCRF = electronic case report form; EUA = emergency use authorization; [REDACTED]; EoT = end of treatment; ET = early termination; ICU = intensive care unit; INR = international normalized ratio; [REDACTED]; PK = pharmacokinetic; RT-PCR = reverse transcription polymerase chain reaction; SARS-CoV-2 = severe acute respiratory syndrome coronavirus 2; [REDACTED]; [REDACTED]

a The treatment duration will be a minimum of 7 days and up to 14 days or day of hospital discharge, whichever one is sooner. Once participants are discharged from the hospital, they will no longer be administered study drug.

b Additional information will be obtained from medical records.

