3.2.4 Participant compliance

The Investigator may withdraw a participant from the study or discontinue study drug for any of the following reasons:

- Noncompliance with protocol procedures, including those relating to administration of study drug
- Occurrence of a serious adverse event (SAE) or intolerable adverse event (AE)
- Occurrence of a clinically significant change in a laboratory parameter

[REDACTED]

[REDACTED]

[REDACTED]

[REDACTED]

[REDACTED]

- Termination of the study by the Sponsor or Investigator
- The participant requests to be discontinued from the study

Participants who discontinue study drug (regardless of reason) will be asked to remain in the study to complete all remaining assessments until hospital discharge or Day 28, whichever is sooner, unless they withdraw consent or are lost to follow-up. If this is not feasible, the participant will be assessed for an early termination visit. All assessments that are required at the last study visit, as shown in [Appendix A](#), should be completed for any participant who is withdrawn from the study or prematurely discontinues study drug and does not agree to complete all remaining assessments.

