12. APPENDIX

12.1 Appendix A: Schedule of Events

	Screening	Treatment Period ^a							EoT/ET	Phone Call ^b	Phone Call ^b
	Day -3 to Day -1	Baseline Day 1	Day 3	Day 5	Day 7	Day 10 ^c	Day 14	Day of Hospital Discharge	Day 28	Day 90	
Informed consent	X										
Medical history	X										
Demographics (age, sex, race)	X										
SARS-CoV-2 infection by RT-PCR or COVID-19 tests authorized under EUA	X										
Serum pregnancy test (for women only)	X	X						X	X		
Check inclusion and exclusion criteria	X	X									
Complete physical examination (including height and weight) ^d	X										
Targeted physical examination ^d		X	X	X	X	X	X	X	X		
Randomization		X									
	X	X	X	X	X	X	X	X	X		
Ventilator utilization ^e											
	X	X	X		X			X	X		
Vital signs ^g	X	X	X	X	X	X	X	X			
	X	X	X	X	X	X	X	X			
Confirm daily conduct of vital signs and safety labs ^h											
Hematology ^{g,h}	X	X	X	X	X	X	X	X			
Clinical chemistry ^{g,h}	X	X	X	X	X	X	X	X			
Coagulation (INR) ^{g,h}	X	X	X	X	X	X	X	X			
Pharmacokinetic sample plasma ⁱ		X			X			X	X		

	Screening	Treatment Period ^a							EoT/ET	Phone Call ^b	Phone Call ^b
		Day -3 to Day -1	Baseline Day 1	Day 3	Day 5	Day 7	Day 10 ^c	Day 14			
Plasma biomarker samples			X	X		X		X	X		
Serum biomarker samples			X	X		X		X	X		
Urinalysis (dipstick, followed up by micro if abnormal)		X	X	X	X	X	X	X	X		
Adverse events											
Concomitant medications											
Study drug administration											
Hospital and ICU utilization ^e											
Vital status									X	X	X

eCRF = electronic case report form; EUA = emergency use authorization; [REDACTED]; EoT = end of treatment; ET = early termination; ICU = intensive care unit; INR = international normalized ratio; [REDACTED]; PK = pharmacokinetic; RT-PCR = reverse transcription polymerase chain reaction; SARS-CoV-2 = severe acute respiratory syndrome coronavirus 2; [REDACTED]

^a The treatment duration will be a minimum of 7 days and up to 14 days or day of hospital discharge, whichever one is sooner. Once participants are discharged from the hospital, they will no longer be administered study drug.

^b Additional information will be obtained from medical records.

^c If participant is no longer being treated with study drug and has been discharged from the hospital, the remaining assessments may be omitted, except for the Day 28 and 90 phone calls and/or medical records.

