^d Physical examinations may be performed if can be done safely. Otherwise nursing assessment or verbal review of systems may be performed.

^e Ventilator utilization, [REDACTED] and ICU utilization to be assessed from medical records after day of hospital discharge.

^f [REDACTED]

^g [REDACTED]

^h Vital signs and local laboratory assessments will be conducted per ICU standards and at least daily. Results from these safety laboratory assessments will be recorded on the days specified.

ⁱ Samples will be collected at the following timepoints:

[figure not shown]
Day 1: 0.5 hours (± 15 min), 3 hours (± 60 min), and 10 hours (± 120 min) postdose

[figure not shown]
Day 7: predose, 3 hours (± 60 min), and 24 hours (± 60 min) postdose

Day 14: predose for participants on study drug

If the participant is no longer being treated with study drug, discontinues the study early, or is not treated with study drug on Day 14, a single plasma sample for PK should be taken at the Day 14/EoT/ET Visit if possible. Actual PK sample collection time and dosing time will be recorded.

- j For participants on hemodialysis, the study drug will be administered after the participant has completed the hemodialysis.

12.2 Appendix B: 

12.3 Appendix C:

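### SAP 7.3 compares arms on a plain incidence of laboratory abnormalities, although the number of recorded draws depends on discharge or death after randomization

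*SAP*

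**What the plan says.** SAP 7.3 states: "The incidence of treatment-emergent laboratory abnormalities will be summarized by severity and treatment group". Protocol 12.5 carries the same sentence. Neither adds a counting rule, a window or a measure of observation. The denominator follows from SAP 7, which bases all safety summaries on the Safety Set. SAP 4.4 leaves missing safety data missing.

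Four provisions decide how many results each participant contributes:

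- SAP 7.3 ties the tests to the visit schedule: "Clinical laboratory tests will be obtained at the time points presented in Appendix A".
- Footnote c of SAP Appendix A ends the schedule early for some: "If participant is no longer being treated with study drug and has been discharged from the hospital, the remaining assessments may be omitted". Only the Day 28 and Day 90 calls and/or medical records then remain. Drug itself ends at discharge at the latest: "The treatment duration will be a minimum of 7 days and up to 14 days or day of hospital discharge, whichever one is sooner" (Protocol Appendix 1, footnote a).
- Hospital laboratory tests are run at least daily, but footnote h says: "Results from these safety laboratory assessments will be recorded on the days specified".
- Extra results do not reach the tables: "Laboratory parameter results from unscheduled visits will be excluded from table summaries but will be included in data listings" (SAP 7.3).

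Adverse events, by contrast, have a stated collection window from consent to Day 28 (SAP 7.2).

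**The concern.** An incidence asks whether something was ever seen, so it grows with the number of looks. Here the number of looks depends on how long the participant stays in hospital and alive, which is what a treatment for ARDS is meant to change. A drug that shortens stay could appear to cause fewer laboratory abnormalities, and one that keeps very ill participants alive in hospital could appear to cause more, with no difference in risk at any given draw. With about 9 participants against 3 in a cohort, chance differences in stay can do the same.

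The daily hospital tests do not even this out, because only results on schedule days are recorded and unscheduled results stay out of the tables. A participant who dies before the first post-baseline draw would count as a non-event in a Safety Set denominator unless the SAP says otherwise.

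**Working it through.** The plan states no laboratory-abnormality rate, so there is no figure of its own to reproduce.

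**Inputs from the documents.** Recorded post-baseline days are 3, 5, 7, 10 and 14, plus a draw on the day of discharge. Day 1 is taken as pre-dose, in line with the baseline definition in SAP 4.6. Allocation is 9:3 per cohort, and SAP 1 says only one cohort remains.

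**Assumed inputs.** The probability p of a new abnormality at each draw is 5%, 10% or 20%, equal in both arms and independent across draws. Lengths of stay are also assumed.

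**Step 1: draws by day of discharge.** Up to Day 3: 1. Day 4–5: 2. Day 6–7: 3. Day 8–10: 4. Day 11–14: 5.

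**Step 2: extreme contrast.** With k draws, expected incidence is 1 − (1 − p)^k. One arm all leaves on Day 7 (k = 3), the other on Day 14 (k = 5):

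| p | Day 7 | Day 14 | gap |
|---|---|---|---|
| 5% | 14.3% | 22.6% | 8 points |
| 10% | 27.1% | 41.0% | 14 points |
| 20% | 48.8% | 67.2% | 18 points |

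**Step 3: overlapping stays.** Let S(d) = 2^(−d/m) be the share staying beyond Day d when stays are exponential with median m. Everyone is given at least one draw, and draws are capped at five. Then incidence = p × [1 + (1−p)S(3) + (1−p)²S(5) + (1−p)³S(7) + (1−p)⁴S(10)].

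- m = 7: S = 0.743, 0.610, 0.500, 0.371. At p = 10%: 0.1 × (1 + 0.669 + 0.494 + 0.365 + 0.244) = 27.7%.
- m = 14: S = 0.862, 0.781, 0.707, 0.610. At p = 10%: 0.1 × (1 + 0.776 + 0.632 + 0.515 + 0.400) = 33.2%.

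The gap is 5.5 points. The same formula gives 14.9% v 18.1% at p = 5% and 47.9% v 56.0% at p = 20%, so 3 to 8 points. If a separate discharge draw after Day 14 is recorded, p(1−p)⁵S(14) is added: at p = 10%, 1.5 and 3.0 points, giving 29.2% v 36.2%.

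**Step 4: direction.** Suppose one arm's participants die around Day 7 to 9, after 3 draws. They match the five-draw arm once their per-draw risk is 1 − (1 − p)^(5/3), which at p = 10% is 16.1%, or 1.6 times as high. With death on Day 6, after 2 draws, the factor is 2.1 to 2.4 over the range of p. Above these values the shorter-observed arm shows the higher incidence.

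**Step 5: sampling error.** For 9 v 3 participants at 27.7% v 33.2%, √(0.277 × 0.723/9 + 0.332 × 0.668/3) = 31 points. In the step 2 contrasts it is 27 to 32 points.

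**Step 6: common window.** Through Day 5, anyone discharged on Day 4 or later has two draws. Incidence is p × [1 + (1−p)S(3)]: at p = 10%, 16.7% v 17.8%. The gap falls from 5.5 to 1.1 points.

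**Step 7: a rate per participant-day.** Dividing participants with an abnormality by days from first dose to last result gives, in the step 2 case at p = 10%, 27.1/6 = 4.5 v 41.0/13 = 3.2 per 100 participant-days. The false difference turns round and is of similar size (ratio 1.43, against 1.51 for crude incidence). Draws are denser early: three by Day 7, two more by Day 14.

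**The case against.** A reader might infer that the arm leaving or dying sooner must show fewer abnormalities. The documents do not support that. It needs equal and independent risk at every draw; sicker participants may have higher risk while observed, and a persistent abnormality makes later draws add little. Nothing shows that one arm leaves sooner, and randomization gives no prior reason to expect it.

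Three further inferences go too far:

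- That the table counts each participant once. This is the natural reading, but the rule in SAP 7.2.5 is written for TEAEs and 7.3 has none.
- That laboratory data end at Day 14 for everyone. The schedule has a column for "Day of Hospital Discharge", the alignment of the last laboratory mark cannot be read with certainty from the extracted table, and participants who stop drug early are asked to "complete all remaining assessments until hospital discharge or Day 28, whichever is sooner" (SAP 3.2.4).
- That uneven observation would be invisible. SAP 7.3 plans by-visit statistics per arm, which include n under SAP 4. Listings include unscheduled results, and disposition and exposure are tabulated.

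Clinically significant findings must also be recorded as adverse events through Day 28 (Protocol 8.7, SAP 7.2). That gives the most important ones a second route, though a laboratory finding still needs a draw.

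These points limit the concern without removing it. The incidence table itself carries no measure of observation, and an unpredictable direction is still a reason to show one.

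**Conclusion.** The point holds in a limited form. The planned incidence compares arms without regard to how often each was observed, and that frequency depends on events after randomization. Under equal per-draw risk the false gap is about 5.5 points at p = 10% with exponential stays of median 7 v 14 days (3 to 8 points for p of 5% to 20%), and 8 to 18 points in the extreme Day 7 v Day 14 contrast. All these risks and stays are assumptions, and the sign can reverse.

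The consequence is modest. SAP 4 and 7 plan no hypothesis test, only one cohort remains, and sampling error at 9 v 3 exceeds any of these gaps. The change is worth making because the table serves the primary safety objective and should be interpretable as shown.

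**What to change.** In SAP 7.3, keep the crude incidence by severity and arm, and add for each arm:

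- (a) the number of participants with at least one post-baseline result, used as the denominator, and the number of post-baseline draws;
- (b) the incidence within an early common window, for example through Day 5 and counting the discharge draw, with the number observed.

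State the counting rule in the same place. Read any between-arm difference in the crude incidence alongside (a) and (b). Do not replace it with participants per 100 participant-days to last result, which is itself biased (step 7).

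The number observed in (b) is needed because complete observation to Day 5 cannot be presumed: under the assumed stays only about 61% (median 7 days) to 78% (median 14 days) remain in hospital beyond Day 5. The window also does not remove selection by death before Day 5.

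The cost is SAP wording and a slightly longer table from data already collected. The early window omits later abnormalities, which remain in the crude incidence and the listings.

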## 12 PLANNED STATISTICAL METHODS

### 12.1 General Considerations

No statistical hypotheses will be tested. Data will be summarized with descriptive statistics. Graphic presentations may also be prepared. All data will be listed by treatment group and participant.

A statistical analysis plan (SAP), which will provide a detailed analysis plan, will be prepared and approved before database lock. Where different, the analyses described in the statistical analysis plan will supersede those described in the protocol.

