### 12.5 Primary Endpoint

The primary endpoint is the nature and proportion of TEAEs between PLN-74809 and placebo groups (descriptive).

Safety data from all participants who received at least one dose of study drug will be incorporated into the final safety analysis. Further details of the safety analyses will be provided in the SAP. AEs will be collected from the time the participant signs the ICF until Day 28. TEAEs are defined as AEs that emerged or worsened in severity after the first administration of study drug.

AEs will be coded using the Medical Dictionary for Regulatory Activities (MedDRA®). All AEs will be graded for severity per the CTCAE grading scale and listed by participant and summarized by last treatment taken at onset of AE. All AEs will be listed by participant and summarized by last treatment taken at onset of AE.

The incidence of AEs, the incidence of TEAEs, the incidence of treatment-related AEs, and the severity of AEs will be summarized by system organ class, preferred term, and maximum severity. In cases where a participant reports multiple occurrences of the same event (preferred term), the greatest severity will be included in the summary. The number and percentage of participants with SAEs and treatment-related SAEs and participants who withdraw prematurely due to an AE will be tabulated by study treatment and dose.

Clinical laboratory test parameters will be graded using the CTCAE grading scale for individual participants and values outside the reference ranges will be flagged. The incidence of treatment-emergent laboratory abnormalities will be summarized by severity and treatment group. For each parameter, summary statistics will be calculated for each measure and summarized by treatment and dose.

[REDACTED]

Vital sign measurements, other laboratory tests, concomitant medications, medical history and changes in physical examinations at each time point will be listed by participant.

[REDACTED]

Concomitant medications will be coded using the most current WHO drug dictionary available.

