4.3 Assessment Windows

All data will be included in the analysis based on the visit recorded in the database.

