4.6 Data Derivations and Transformations

The following derivations will be used in this study:

Study day:

- Date of assessment – date of study drug administration + 1 for assessments done on or after date of study drug administration
- Date of assessment – date of study drug administration for assessments done before date of study drug administration

Baseline value: the last non-missing value prior to study drug administration.

Shift from baseline: current value – baseline value. Although generally reserved for quantitative variables, it is also applied to some numeric ordinals

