In the remaining summary tables, the incidence of TEAEs will be calculated by dividing the number of participants who have experienced the event by the total number of participants in the Safety Set. Thus, the incidence of TEAEs is shown in terms of the total number of participants and not in terms of the total number of episodes. If a participant has repeated episodes of a particular TEAE, only the most severe episode, or the episode with the strongest causal relationship, will be counted in the summary tables.

A participant with more than one type of TEAE in a particular SOC or PT will be counted only once in the total of participants experiencing TEAEs in that particular SOC or PT.

All occurrences of all AEs and SAEs will be listed for each participant, grouped by treatment arm. The listing will contain the following information: treatment arm, verbatim term, SOC, PT, severity, related to investigational product, related to trial procedure, date and day of onset, date and day of resolution, action taken with regard to study drug, treatment given to treat the adverse event, the outcome, whether the event was an SAE, SAE criteria (if applicable), whether it led to study withdrawal, and whether it is a TEAE. Listings will be sorted by treatment arm, participant identification number, onset date, SOC, and PT. If the onset date is completely missing, then these events will be presented first. If the onset date is missing a month or a day, then these events will be presented before any complete dates.

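### The by-visit exclusions in SAP 7.3 also reach the laboratory-abnormality incidence table, so participants' worst grades may be understated

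*SAP*

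**What the plan says.** SAP 7.3 describes two kinds of laboratory table. The first is categorical: "The incidence of treatment-emergent laboratory abnormalities will be summarized by severity and treatment group". The second gives descriptive statistics of raw and change-from-baseline values at each time point. The next paragraph sets two handling rules:

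- **Unscheduled results:** "Laboratory parameter results from unscheduled visits will be excluded from table summaries but will be included in data listings".
- **Repeats:** "When there are repeat measurements for a given visit, only the last measurement will be used in the table summaries".

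Four other places bear on the point:

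- SAP 4.3 sets no date windows: "All data will be included in the analysis based on the visit recorded in the database".
- SAP 4.6 defines baseline as "the last non-missing value prior to study drug administration", with no limit to scheduled samples.
- SAP 7.2.5 says that for a recurrent TEAE "only the most severe episode, or the episode with the strongest causal relationship, will be counted in the summary tables".
- Protocol 12.5 plans the same laboratory incidence table without these exclusions ("Clinical laboratory test parameters will be graded using the CTCAE grading scale for individual participants and values outside the reference ranges will be flagged"). Protocol 12.1 settles which document governs: "Where different, the analyses described in the statistical analysis plan will supersede those described in the protocol".

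**The concern.** Dropping unscheduled results and keeping one value per visit is ordinary practice for by-visit means, where each participant should contribute one comparable value. An incidence table by severity asks something different: how bad a participant's value became at any time after dosing. Its usual basis is the worst value, and these rules can remove exactly that value.

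The excluded results are not a random subset. Protocol 7.11.1 calls for follow-up testing of clinically significant new abnormalities, so extra results tend to come from participants who already have a laboratory problem. A participant whose peak was on an unscheduled sample, or was followed by a milder repeat at the same visit, is tabulated at a lower grade or as having no abnormality.

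Safety is the primary objective and laboratory parameters are a named safety assessment (SAP 7). The listings would still show the value, but they give no incidence. Under Protocol 8.7 an abnormal result is not in itself an AE, so the AE tables recover only part of what is lost.

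**Working it through.** The plan states no figure to reproduce: no hypothesis is tested and the sample-size text is redacted. The check is a reading of the rules, a direction argument and some labelled illustrations.

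**1. Scope.** Both rules refer to laboratory table summaries in general. The incidence table is introduced in the paragraph just before them. No section exempts it or gives a worst-value rule, and SAP 4.3 does not move an unscheduled sample to a nearby scheduled visit.

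**2. Direction.** For one participant and one parameter, let A be the grades of all recorded post-baseline results and S the subset left after the two rules. Since S is contained in A, max(S) ≤ max(A). With the baseline grade fixed, the count at or above any grade cannot rise. A cell for one exact lower grade can rise, because participants drop into it.

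**3. Constructed example.**

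| Result | Grade | Kept under SAP 7.3? |
|---|---|---|
| Day 3, first | 3 | No (repeated) |
| Day 3, repeat | 1 | Yes |
| Day 5 | 1 | Yes |
| Day 6, unscheduled | 4 | No |
| Day 7 | 2 | Yes |

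The tabulated worst grade is max(1, 1, 2) = 2. Over all results it is 4.

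**4. Weight of one participant.** SAP 3.1 plans 9 active and 3 placebo per cohort. SAP 1 says only one cohort was enrolled and does not give its actual size. On planned numbers, one missed participant is 1/9 = 11.1 points (active) or 1/3 = 33.3 points (placebo).

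**5. Simple illustration (p and q are assumptions).** Let p be the true Grade 3+ incidence and q the share of those participants whose Grade 3+ results are all on excluded records. Tabulated incidence is p(1 − q). The chance that at least one of 9 active participants is missed is 1 − (1 − pq)^9.

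| p | q | Tabulated | Chance of ≥1 of 9 missed |
|---|---|---|---|
| 0.10 | 0.10 | 9.0% | 1 − 0.99^9 = 8.6% |
| 0.20 | 0.25 | 15.0% | 1 − 0.95^9 = 37.0% |
| 0.40 | 0.50 | 20.0% | 1 − 0.80^9 = 86.6% |

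**6. Hypothetical simulation of the last-repeat rule alone.** Assumed: log-normal marker with median 1×ULN, between-participant log-SD 0.5 or 0.7, within-participant CV 10%, 20% or 30%, five post-baseline visits, a flag above 3×ULN (the multiple is borrowed from inclusion criterion 11), and a share r of flagged values repeated at the same visit. One million participants were simulated per setting.

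| r | Ever-flagged participants who vanish from the table |
|---|---|
| 0 | 0% |
| 0.25 | 4–13% |
| 0.50 | 8–27% |
| 1.00 | 19–63% |

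The absolute loss is at most 6.4 percentage points. In a single-visit version, a repeat falls back to or below the threshold in 15.8–61.4% of cases. Among those, the median first value is 3.2–3.5×ULN, and 58–85% come from participants whose underlying level is at or below the threshold.

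**The case against.** The strongest reply is that the rules were meant only for the by-visit statistics. They follow the sentence on those statistics, the repeat rule speaks of a given visit, and SAP 7.4 has a similar exclusion that applies only to by-visit vital-sign summaries. That may well be the intent, but the text does not say so, and a programmer following it would apply the rules to both tables.

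Other points stand in part:

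- **Direction depends on baseline.** If the rules were also applied to pre-dose values, a baseline grade could fall and a treatment-emergent count could rise. SAP 4.6 states no such limit, so the direction holds on the definition as written.
- **Many off-schedule results may never be recorded.** The schedule of events has laboratory tests done at least daily but recorded only on specified days. This may shrink what the unscheduled rule removes, and no tabulation rule recovers unrecorded data.
- **The most consequential values have another route.** Abnormalities that are clinically significant, or come with signs or symptoms, are recorded as AEs if they meet the AE definition. SAP 7.2.5 tabulates TEAEs by greatest severity and at Grade 3 or above. In one small cohort the listings can also be read in full.
- **Protocol 12.5 is silent on these rules and leaves detail to the SAP.** The difference is not a conflict. It shows only that the protocol does not supply the missing worst-value rule.
- **The simulation says nothing about this trial's rates.** Its inputs are assumed, its upper range needs every flagged value to be repeated, and most of the values it loses are borderline.

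These points limit the consequence. They do not supply the missing scope statement.

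**Conclusion.** The point holds. As written, SAP 7.3 applies two by-visit rules to a table that should show the worst grade, and the counts at or above a grade can be understated. This rests on three things: the literal scope of the rules, baseline fixed as in SAP 4.6, and the usual reading that each participant is counted at the highest grade, which the SAP should itself state.

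The size cannot be derived from the documents. It is zero if no excluded value is worse than a tabulated one, and the 11- and 33-point figures assume the planned 9:3 split. The consequence is confined to a descriptive laboratory-safety table. It should be fixed because the correction is cheap and brings the laboratory table into line with the SAP's own most-severe-episode rule for AEs.

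**What to change.** In SAP 7.3:

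1. State that both rules apply only to the by-visit descriptive statistics of continuous values.
2. Build the incidence table from each participant's worst post-baseline CTCAE grade per parameter, over all recorded results: scheduled, unscheduled and every repeat.
3. Count an abnormality as treatment-emergent when that grade exceeds the baseline grade, with baseline as in SAP 4.6.
4. Show the number of recorded post-baseline results per participant, by arm, beside the table.

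The cost is the wording, one derived worst-grade variable and one count column, with no new data. The drawback is that a worst grade rises with the number of tests and picks up borderline noise, so an arm tested more often may look worse. The counts in item 4 make this visible but do not remove it.
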